7.1.1 Serious Adverse Event (SAE) Definitions

An AE that (related or not related to the investigational test articles, comparator products or study procedures):

• Led to death

- Led to serious deterioration in the health of the subject, that resulted in:
 - A life-threatening illness or injury; or
 - A permanent impairment of a body structure or a body function (e.g., blindness); or
 - Inpatient or prolonged hospitalization; or
 - Medical or surgical intervention to prevent life-threatening illness or injury or permanent impairment to a body structure or a body function
- Led to fetal distress, fetal death, or a congenital abnormality or birth defect.

Note: A planned hospitalization for a pre-existing condition, or a procedure required by the protocol, without serious deterioration in health, is not considered an SAE.

Serious adverse events may include but are not limited to any hazardous, sight-threatening conditions occurring after exposure to the investigational test article or control product including, but not limited to, the following:

- A presumed infectious ulcer (defined as a progressive erosion of the corneal tissue). For the purposes of reporting, this includes:
 - Central or para-central location
 - Penetration of Bowman's membrane
 - Infiltrate $\geq 2 \text{ mm diameter}$
 - Associated with iritis
 - Associated with any increase in intraocular pressure
 - Culture positive for microorganisms
 - Increasing size or severity at subsequent visits

NOTE: Signs of a presumed infectious corneal ulcer may include irregular focal infiltrates, active lesions with raised edges, significant diffuse infiltration, anterior corneal to mid-stromal involvement, erosion with overlying staining, conjunctival and lid edema, anterior chamber reaction (iritis), and severe bulbar and limbal redness. Symptoms associated with a presumed infectious ulcer (microbial keratitis) may include pain of rapid onset, severe redness, purulent or mucopurulent discharge, tearing, and photophobia.

- Any central or paracentral (within the central 6 mm of cornea) corneal event that results in permanent opacification (such as corneal scar or vascularization)
- Any serious adverse ophthalmic events including hypopyon and/or hyphema
- Any neovascularization within the central 6 mm of the cornea
- Permanent loss of ≥ 2 lines of BSCVA
- All cases of iritis.

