- 0 None: No hyperemia present. Normal appearance of limbal vessels including prominent limbal vascular arcades.
- 1 Trace: Very slight hyperemia of limbal vessels in one quadrant.
- 2 Mild: Mild hyperemia of limbal vessels in more than one quadrant.
- 3 Moderate: Marked hyperemia of limbal vessels in any quadrant.
- 4 Severe: Marked hyperemia of limbal vessels in all quadrants

Bulbar Injection

- 0 None: No hyperemia present. Normal appearance of conjunctival vessels.
- 1 Trace: Slight hyperemia of conjunctival vessels in one quadrant.
- 2 Mild: Mild hyperemia of conjunctival vessels in more than one quadrant.
- 3 Moderate: Marked hyperemia of conjunctival vessels in any quadrant.
- 4 Severe: Marked hyperemia of conjunctival vessels in all quadrants.

Upper Lid Tarsal Conjunctival Abnormalities

- 0 None: Normal, velvet tarsal conjunctival appearance. No hyperemia or enlarged papillae.
- 1 Trace: Slight tarsal conjunctival hyperemia with slight loss of smoothness.
- 2 Mild: Slight tarsal conjunctival hyperemia with slight loss of smoothness. Noticeable enlargement of papillae, but less than 1.0 mm in diameter.
- 3 Moderate: Definite loss of smoothness with enlarged papillae, but less than 1.0 mm in diameter with marked tarsal conjunctival hyperemia.
- 4 Severe: Localized or generalized giant papillae, larger than 1.0 mm in diameter and/or severe tarsal conjunctival hyperemia.

Corneal Neovascularization

- 0 None: Normal appearing limbus, including prominent limbal vascular arcades.
- 1 Trace: Vascularization less than 1.0 mm of advancement into cornea in one quadrant.
- 2 Mild: Vascularization greater than 1.0 mm to less than 1.5 mm of advancement into cornea in more than one quadrant.
- 3 Moderate: Vascularization greater than 1.5 mm to less than 2.0 mm of advancement into cornea in any quadrant.
- 4 Severe: Vascularization more than 2.0 mm of advancement into cornea in any quadrant.

Corneal Infiltrates

- 0 None No infiltrates.
- 1 Trace single or multiple epithelial infiltrates < 1 mm in diameter.
- 2 Mild single or multiple epithelial infiltrates ≥ 1 mm and < 2 mm in diameter.
- 3 Moderate multiple infiltrates $\geq 2 \text{ mm and } < 3 \text{ mm in diameter.}$
- 4 Severe multiple dense infiltrates ≥ 3 mm in diameter.

Infiltrate Size (Largest): OD: (X.X mm) OS: (X.X mm)

Infiltrate Depth (Deepest):

OD: OS:

- 1. E Epithelial
- 2. AS Anterior Stroma
- 3. P mid/posterior stromal

Infiltrate Density:

Grade Description

- 0 None
- Faint 1

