#### 4.5.1. Definition of Endpoints

The safety-related endpoint is as follows:

- The proportion of eyes with any slit-lamp findings greater than Grade 2 over all follow-up visits (scheduled and unscheduled).
  - At each follow-up visit, graded slit-lamp findings will be assessed for each eye using Grades 0 through 4. Using only the non-missing observations from all follow-up visits, each eye will be classified with respect to findings greater than Grade 2 at any visit (Absent, Present).

The efficacy-related endpoints are as follows:

- Overall comfort averaged over all scheduled follow-up visits.
  - At each follow-up visit, overall comfort will be assessed for each eye on a scale from 0 to 100, with 100 denoting the most favorable response. For each eye, mean overall comfort over all follow-up visits will be computed as the average of the non-missing values over all scheduled follow-up visits
- Vision averaged over all scheduled follow-up visits.
  - At each follow-up visit, vision will be assessed for each eye on a scale from 0 to 100, with 100 denoting the most favorable response. For each eye, mean vision over all follow-up visits will be computed as the average of the non-missing values over all scheduled follow-up visits.
- The proportion of eyes with a maximum degree of front surface deposits grade of  $\leq 2$  over all scheduled follow-up visits.
  - At each follow-up visit, the degree of front surface deposits will be graded for each eye as 0, 1, 2, 3, or 4. Using only the non-missing observations from scheduled follow-up visits without imputation, each eye will be classified with respect to the maximum grade of front surface deposits ( $\leq 2$ ,  $> 2$ ) observed over all follow-up visits.

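### The corneal-infiltrate scale has no grade for a single infiltrate of 2 mm or more, so the primary safety endpoint can miss such an eye: a minor defect that one derivation line would close

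*Protocol*

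**What the plan says.** Protocol Appendix B 2.0 grades corneal infiltrates from 0 to 4:

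- Grade 1: "single or multiple epithelial infiltrates < 1 mm in diameter"
- Grade 2: "2 Mild single or multiple epithelial infiltrates ≥ 1 mm and < 2 mm in diameter"
- Grade 3: "3 Moderate multiple infiltrates", from 2 mm to below 3 mm
- Grade 4: "4 Severe multiple dense infiltrates ≥ 3 mm in diameter"

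The same form records the size in millimetres separately from the grade: "Infiltrate Size (Largest): OD: (X.X mm) OS: (X.X mm".

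The primary safety endpoint (Protocol 8.1.4 and 8.6.1.5; SAP 4.5.1) is built from the grades. Using non-missing observations only, SAP 4.5.1 states that "each eye will be classified with respect to findings greater than Grade 2 at any visit (Absent, Present". SAP 4.1.4 and 4.5.1 include unscheduled follow-up visits. Test succeeds if the Newcombe-Wilson upper 97.5% limit for Test minus Control is below 5.0%, or if neither group has any such finding. Neither document has a rule for an infiltrate that fits no grade.

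**The concern.** Number and size change together between Grades 2 and 3, and one combination is left out. A lone infiltrate of 2 mm or more is too large for Grade 2 and is not *multiple*, as Grades 3 and 4 require. The word stands in both upper grades, so it is unlikely to be an artefact of text extraction. The gap begins at the point where the endpoint switches from absent to present.

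The grader must then choose. Grade 3 by size counts the eye. Grade 2 by number, or a blank, does not count it unless another finding exceeds Grade 2. If Test caused more such infiltrates than Control, uncounted eyes would shrink the difference and favour non-inferiority on safety.

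The planned sensitivity analyses would not correct a misgraded eye. The best/worst-case and tipping-point analyses in SAP 4.5.3 act on missing values, and an infiltrate entered as Grade 2 is not missing. Adverse events do not substitute for the endpoint either: Protocol 5.1 gives their rate no success criterion, and SAP 4.8.1 rules out statistical testing of them.

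**Working it through.** **1. The grades side by side (Protocol Appendix B 2.0)**

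| Grade | Number | Other condition | Largest diameter |
|---|---|---|---|
| 1 | single or multiple | epithelial | < 1 mm |
| 2 | single or multiple | epithelial | 1 to < 2 mm |
| 3 | multiple | none | 2 to < 3 mm |
| 4 | multiple | dense | ≥ 3 mm |

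- One infiltrate of 2.5 mm fails Grades 1 and 2 on size, Grade 3 on number, and Grade 4 on both. It has no grade.
- Several non-dense infiltrates of 3.5 mm fail Grade 3 on size and Grade 4 on density. They have no grade. Both neighbouring grades lie above the cut, so this gap affects the endpoint only if the eye is left ungraded or graded well below its size.

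**2. The plan's own power figure**

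Inputs (Protocol 8.3.4, SAP 2.2.4): 300 eyes per arm, rate 0.008 in both arms, margin 0.05, one-sided 97.5% Newcombe-Wilson limit, eyes independent. Exact enumeration over two Binomial(300, 0.008) arms gives 99.94% power, against the stated 99%. The plan's figure reproduces, and this point does not change it. Expected events per arm: 0.008 × 300 = 2.4.

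**3. Where the decision turns**

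Upper limit = (p_T − p_C) + √[(u_T − p_T)² + (p_C − l_C)²], where u_T is the upper Wilson limit for Test and l_C the lower Wilson limit for Control. With 2 Control events, p_C = 0.00667 and l_C = 0.00183.

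- 9 Test events: p_T = 0.03000, u_T = 0.05602. Limit = 0.02333 + √(0.02602² + 0.00484²) = 0.0498, or 4.98% (pass).
- 10 Test events: p_T = 0.03333, u_T = 0.06026. Limit = 0.02667 + √(0.02693² + 0.00484²) = 0.0540, or 5.40% (fail).
- With 3 Control events, 9 pass (4.68%) and 10 fail (5.11%).
- The Safety Population is all dispensed subjects, up to about 340 eyes per arm. At that size, with 2 Control events, 10 pass (4.78%) and 11 fail (5.15%).

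**4. How likely the trial is to sit on that boundary**

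For 300 eyes per arm, the largest passing Test count is 7, 8, 9, 9 and 10 for 0, 1, 2, 3 and 4 Control events. One extra Test event changes the result only if Test lands exactly on that count. Summing P(Control = c) × P(Test = that count) at a rate of 0.008:

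0.072% + 0.052% + 0.016% + 0.013% + 0.002% = 0.155%, about 0.16%. Higher Control counts add almost nothing.

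**5. Range if Test were truly worse**

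The documents give no frequency for these infiltrates, so the excess below is an assumption. The Control rate stays at 0.008. The last column is the extreme case in which every excess Test event is such an infiltrate and every one goes uncounted.

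| Assumed excess in Test | Excess eyes per 300 | Chance of passing, all counted | Chance of passing, all excess lost |
|---|---|---|---|
| 0.33 points | 1 | 99.5% | 99.9% |
| 1 point | 3 | 93.8% | 99.9% |
| 2 points | 6 | 64.7% | 99.9% |
| 3 points | 9 | 29.5% | 99.9% |

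The effect is negligible at one eye and would be material only with several lost eyes, all in one arm.

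**The case against.** The opposing case accepts the wording gap and disputes its consequence. Most of it stands.

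- **Grading by size is plausible.** The four size bands are contiguous, and Grade 2 for a lesion of 2 mm or more would breach that grade's own upper bound. An investigator may well enter Grade 3. This makes the error less likely, but it does not supply the missing rule.
- **Other signs may count the eye.** An eye with an infectious ulcer would probably also exceed Grade 2 on staining or injection: Appendix B gives erosion with epithelial loss staining Grade 4 and marked hyperaemia Grade 3. What remains exposed is the eye with a large infiltrate and no other finding above Grade 2 at any follow-up visit.
- **A blank grade should be queried.** Protocol 9.4 requires omissions to be explained, full source verification and edit checks. That answers the blank-grade route only; a query does not say which grade is right.
- **The information is not lost to the trial.** Size, depth, density and location are recorded and summarised (SAP 4.9), and symptomatic infiltrative events are significant adverse events (Protocol 7.1.2). What can be lost is a count in the endpoint that decides safety success.
- **Sites may have been instructed.** Appendix B allows procedural changes under separate cover, and Protocol 2.6 promises standardised training. Neither is visible here, so it cannot be said that each site is left to choose.
- **The boundary counts are far from plan.** Nine or ten Test events is about four times the expected 2.4; nine or more has a probability of about 0.08% at the planned rate. With 2 Control events, every Test count from 2 to 8 passes comfortably (1.80% to 4.55%).

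Two stronger readings are tempting, and the documents support neither. A reader might infer that the scale contradicts the serious-event definition, because Protocol 7.1.1 mentions an infiltrate of 2 mm or more. That size is listed there as a feature of "A presumed infectious ulcer (defined as a progressive erosion of the corneal tissue"), not as a serious event in itself, and a scale that assigns no grade assigns no conflicting seriousness. A reader might also infer that the *epithelial* wording of Grades 1 and 2 matters to the endpoint. A stromal infiltrate below 2 mm does lack a literal grade, but its size puts it below the cut.

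**Conclusion.** The gap is certain from the text and lies at the cut of a primary endpoint. A single infiltrate of 2 mm or more **can** be missed; nothing in the documents shows that it **will** be. A miss requires an infiltrate that fits no grade, an entry of Grade 2 or no grade, and no other finding above Grade 2 in that eye at any follow-up visit. The direction is towards non-inferiority only to the extent that the lost events are excess events in the Test arm.

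The likely effect on the conclusion is small: about a 0.16% chance, at the planned rates, that one extra Test event would reverse a pass. This rests on 300 eyes per arm, a rate of 0.008 in both arms, and the plan's assumption that eyes are independent. The chance would be larger if Test were truly worse. This is a minor defect in the endpoint definition, worth correcting because correction costs almost nothing.

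**What to change.** Before unmasking:

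1. Add to SAP 4.5.1 that any eye whose recorded largest infiltrate is 2.0 mm or more at any follow-up visit, scheduled or unscheduled, is classified as having a finding above Grade 2, whatever the number or density of infiltrates. Record the change in SAP 4.10. Protocol 8.0 allows documented changes at this stage.
2. Align Appendix B 2.0 with that rule: make Grades 3 and 4 cover single or multiple infiltrates, and resolve the density condition so that non-dense infiltrates of 3 mm or more have a grade.

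The cost is one derivation line and a wording correction. No new data are needed, because the form already records the largest size. The event count may rise slightly in both arms.

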5.0 Symptoms/Complaints Rating Scales

For completion of the Symptoms/Complaints Rating Scale Form (conducted at Screening/Dispensing for the subject's habitual lenses and all follow-up visits with the study lenses), the Investigator or designee will obtain Subject responses according to the following procedure for the specific symptoms listed in the Symptoms/ Complaints Rating Table (below):

- Step 1: Ask the Subject: "Are you experiencing any Symptoms or problems with the lenses?"
- **Step 2:** If the Subject answers "*No*", enter "0" on the subject source documentation for all symptoms.
- **Step 3:** If the Subject answers "*Yes*", then ask: "*What specifically are you noticing*". Note that the subject will not be shown the list of options / descriptions.
- **Step 4:** From the Subject's response, select the most appropriate symptom (from the Symptoms/Complaints Rating Scale Table below) and ask the Subject to rate the symptom on the following scale:
- 0 None
- 1 Slight symptoms. The symptom is felt or noticed occasionally.
- 2 Mild symptoms. The symptom is noticeable but not irritating or limiting use.
- 3 Moderate symptoms. The symptom is moderately irritating or annoying; the use of device is limited by <25% (short wear time, etc.).
- 4 Severe symptoms. The symptom is very irritating or annoying, and the lens cannot be tolerated.

Symptoms/Complaint Rating Table

Symptom	OS (left eye)	OD (right eye)
Discomfort	0-4	0-4
Excessive tearing	0-4	0-4
Photophobia	0-4	0-4
Halos	0-4	0-4
Itching/Burning	0-4	0-4
Spectacle Blur	0-4	0-4
Variable Vision	0-4	0-4
Blurred Vision	0-4	0-4
Lens needs cleaning	0-4	0-4
Handling	0-4	0-4

6.0 Subject Assessment Questionnaire

For completion of the Subject Assessment Questionnaire (conducted at Exit Visit), the Investigator or designee will instruct the subject to complete the form according to the care system care system that they have been using during the study. For each statement, the subject will check the box next to the appropriate number from 1 to 6, with 1 = strongly disagree and 6 = strongly agree. Boxes one through three will also be visibly grouped into a category named "disagree," while boxes four through six will be labeled as "agree." The statements are as follows:

- My lenses feel clean upon insertion
- Makes my lenses feel clean throughout the day
- Makes my lenses feel comfortable upon insertion
- Makes my lenses feel comfortable throughout the day
- Helps prevent dryness and discomfort
- My vision remains clear throughout the day
- Feels as gentle as natural tears
- Makes my lenses feel moist throughout the day
- Makes my lenses feel like a fresh pair
- Keeps my eyes feeling healthy
- Gives me a feeling of freedom to wear my lenses worry-free
- Provides long lasting comfort

7.0 Lens Performance Rating Scales

For completion by Subjects. Refer to Rating Scales (separate document) that should be provided to subjects to reference while completing form. Enter rating from 0-100 (e.g., 90).

Lens Performance Rating Scale	Scale Number		
Burning and Stinging Upon Lens Insertion	1		
Comfort Upon Insertion	2		
Overall Comfort	3		
Comfort at the End of Day	4		
Ease of Handling/Insertion	5		
Ease of Handling/Removal	6		
Dryness	8		
Vision Upon Insertion	11		
Vision	12		
Vision in Low Light	13		
Vision at End of Day	26		
Lens Cleanliness Upon Removal	15		
Overall Impression	19		

Abbreviated Lens Performance	Scale Number		
Rating Scale	Scale Mulliber		
Burning and Stinging Upon Lens Insertion	1		
Comfort Upon Insertion	2		
Ease of Handling/Insertion	5		

8.0 Culture Procedures

NOTE: The site must use their standard of care culture kit and ship specimens to their local laboratory for testing per the local labs required procedures. Hard copy results must be filed in the subject record and entered into the eCRF.

PROCEDURES FOR THE INVESTIGATOR

A. In the case of corneal ulcer or suspected ocular infection, the cul-de-sac, lower lid margin, and the corneal lesion (if applicable) of the affected eye must be cultured.

1. Cul-de-sac Culture

- a. The swab from the culture collection kit (provided by the central laboratory) is moistened in sterile, physiological saline solution, with no preservatives.
- b. The ocular specimen is obtained by holding the lids open and asking the subject to gaze upward. The moistened swab should be drawn across the cul-de-sac while rotating the swab 360 degrees around the axis of the stick. Care should be taken to avoid contact of the swab with the lashes and the lid margins.
- c. Place the swab in the transport tube media according to manufacturer's directions.
- d. Repeat Steps a through c using a separate swab and a separate tube of transport media for the other eye if both eyes require culturing.

2. Eyelid Culture

- a. The swab from the culture collection kit (provided by the central laboratory) is moistened in sterile, physiological saline solution, with no preservatives.
- b. The specimen is obtained from the margin of the lower lid by drawing the swab along the margin of the lid.
- c. Place the swab in the transport tube media according to manufacturer's directions.
- d. Repeat Steps a through c using a separate swab and a separate tube of transport media for the other eye if both eyes require culturing.

3. Corneal Culture

- a. The swab from the culture collection kit (provided by the central laboratory) is moistened in sterile, physiological saline solution, with no preservatives.
- b. The specimen is obtained from the corneal lesion by rotating the swab on the lesion for 10 seconds.

- c. Place the swab in the transport tube media according to manufacturer's directions.
- d. Repeat Steps a through c using a separate swab and a separate tube of transport media for the other eye if both eyes require culturing.

APPENDIX C: SUBJECT INSTRUCTIONS

SUBJECT INSTRUCTIONS

PLEASE READ THESE INSTRUCTIONS CAREFULLY AND KEEP FOR FUTURE USE. DO NOT BRING WITH YOU TO THE FOLLOW-UP VISITS.

You will be participating in a study evaluating the clinical performance of two multi-purpose soft contact lens care solutions. Please keep all appointments and **follow these instructions thoroughly**. If you have any questions or problems, call your eye care practitioner. Remember to bring your glasses to all examinations.

NOTE: Wear your study lenses to each of your follow-up visits.

STUDY PRODUCT INFORMATION:

For this study, you will be using the following products:

- Study Contact Lenses.
 - You will be provided with new pairs of your current contact lenses at the start of the study, and then again at the 1-Month and 2-Month Follow-Up Visits.
- A Study Kit. You will be provided with a Study Kit at each visit that will contain:
 - **1 bottle of Study Solution inside a white carton.** Each bottle and each carton will have an investigational label including the Study Kit number (a unique 5-digit number).
 - Study Lens Case. A study lens case will be included with each carton of study solution for you to use for the month. You are required to use this study lens case.
 - o Subject Instructions. Will be provided by unmasked designee with each carton of study solution.
 - o All items, bottle, carton and lens case must be kept and returned at each visit.
- Other Study Supplies. The following supplies will be provided to you as needed:
 - Carton/Bottle Return Materials. Comprised of opaque bags and pre-printed labels for return of Study Kit and worn lenses to the study Investigator.
 - Rewetting Drops: Bausch + Lomb renu® Contact Lens Moisture Drops

IMPORTANT SUBJECT INSTRUCTIONS:

This is a "masked" clinical study in which the Investigators and Coordinators cannot see the Study Solutions that are dispensed to you. There will be a special study employee – the "unmasked designee" – at the site who will dispense all study materials to you in a white opaque bag and who will handle any questions you have related to the study materials.

It is very important that you bring the study solutions or lens cases to the study site in the white opaque bag.

SUBJECT INSTRUCTIONS (continued)

GENERAL INFORMATION:

- Do NOT use any products other than those listed above or dispensed to you by your study doctor for use in this study.
- Do NOT use any other care products other than those listed above.
- Do Not use any topical ocular medications (eye drops) during this study.
- Do NOT discuss or show the dispensed study products to the Investigator or site staff during the study.
- Please save all study materials, both bottles and cartons, during the course of the study, and plan to bring
 study solution with you to each visit. Place the solution bottle back into the carton. Place the carton
 containing the bottle and contact lens cases into the white opaque bag provided.
- Always wash and rinse your hands before you handle your lenses.
- Always handle the same lens (right or left) first, to avoid mix-ups.
- Always keep the products tightly closed when not in use.
- Since you are wearing your lenses on a daily wear basis, you will be using the **Study Solution** daily to clean, rinse, disinfect and store your lenses.

PRECAUTIONS:

- Lens care procedures recommended by your practitioner must be followed.
- Failure to follow these procedures may result in the development of serious eye infections.
- Discard the Study Solution from the lens case after each use.
- Store Study Solution at room temperature.
- Use Study Solution before the expiration date marked on the bottle label and carton.
- Do not use any eye medication in conjunction with this Study Solution unless under medical supervision.
- Do not touch the bottle tip of the **Study Solution** to any surface or to your eye since this may contaminate the solution.
- Keep the Study Solution cap closed when not in use to avoid contamination or evaporation.
- Do not use Study Solution with a heat disinfection method.
- Keep Study Solution out of reach of children.
- Consult with your study eye care practitioner if you have any allergies that may affect your ability to use a multi-purpose solution.

IMPORTANT:

• If irritation or excessive tearing occurs, persists, or increases, or if vision is impaired, discontinue use and promptly consult your study Investigator.

SUBJECT INSTRUCTIONS (continued)

When used as directed, the **Study Solution**: (1) Cleans, loosens, and removes accumulations of film, protein andother deposits from soft contact lenses, and (2) Rinses and stores your soft contact lenses.

GENERAL INSTRUCTIONS:

- Always wash and rinse your hands before you handle your contact lenses.
- · Lenses must be thoroughly cleaned, rinsed, and soaked each time they are removed to achieve disinfection.
- Rinse each case well with the Study Solution before and after each use.

LENS CLEANING INSTRUCTIONS (RUB REGIMEN):

FOR DAILY CLEANING/PROTEIN REMOVAL DISINFECTION AND STORING

- Remove the right lens from your right eye.
- Place at least 3 drops of Study Solution on each side of lens surface and gently rub for 20 seconds.
- Thoroughly rinse each side of the lens for 5 seconds with Study Solution.
- Place the cleaned contact lens in the lens case and fill with fresh Study Solution. Soak at least 4 hours. Remember to always use fresh solution – discard solution from lens case after each use

Your lenses are now ready for wear. If any debris remains on contact lenses, rinse with **Study Solution** prior to insertion.

STUDY LENS CASE CARE:

- · Before first use, rinse lens case and caps thoroughly with Study Solution and allow to dry.
- Clean, rinse and air-dry your lens case each time you remove your lenses. To permit excess solution to drain, flip over your lens case while air drying.
- For visits to the clinic, you need to bring the lens case to the study site.
- Place the lens case in the opaque bag for transfer to the study site.

REWETTING:

- If necessary, you can use the supplied Bausch + Lomb renu® Contact Lens Moisture Drops while wearing your lenses. Simply place 2 or 3 drops of Bausch + Lomb renu® Contact Lens Moisture Drops on contact lens whenever needed. Blink several times.
- If the lens still does not feel comfortable, add another drop.
- If discomfort persists, IMMEDIATELY remove your lens and contact your study Investigator immediately.

WEEKLY CARE:

No separate protein remover is required to remove protein deposits from the lenses. Daily use of Study Solution as directed removes protein.
